3.2.3 Hematologic toxicity Dose adjustments and reductions

Variable	Finding		Dose modification
	Platelets	ANC	

Variable	Finding		Dose modification
	Platelets	ANC	
Hematologic toxicity (based on previous cycle nadir*)	$\leq 25.0 \times 10^9/L$	$\leq 0.5 \times 10^9/L$	Decrease by $20\text{mg}/\text{m}^2$ dose
Delayed recovery for Retreatment due to hematologic toxicity**	Less than or equal to 6 weeks		No change in dose level
	Between 6 and 8 weeks		Decrease by $20\text{mg}/\text{m}^2$ dose
	More than 8 weeks		Off-study
Neutropenic fever			Decrease by $20\text{mg}/\text{m}^2$ dose***

*Complete blood counts must be available on a weekly basis in the previous course

**Time from Day 1 of prior cycle.

***Growth factor support may be given for subsequent cycles as clinically indicated

3.2.4 Retreatment guidelines:

If satraplatin dosing is interrupted during a treatment cycle, it may be restarted as long as the planned 5 days of dosing occurs within an 8-day period (maximum interruption=3 days).

If there is more than a 3 consecutive day delay, no further doses should be given in the cycle.

The patient will be allowed to begin the next cycle a minimum of 35 days after the first day of the previous cycle if the criteria for re-treatment are met.

Patients may be retreated every 35 days if the following criteria are met:

- Hematologic toxicity-Absolute neutrophil count is $\geq 1.5 \times 10^9/L$ and platelets $\geq 100 \times 10^9/L$
- Non-hematologic toxicity ascribed to study drugs must resolve to baseline or \leq grade 1, with the exception of alopecia; or \leq grade 2 for pain in order for re-treatment to continue.

Laboratory tests may be performed up to 48 hours prior to the scheduled study visit and if the retreatment criteria are met, the patient may be retreated. If the re-treatment criteria are not met, the patient may not be retreated until they are met. If therapy has to be held for more than 8 weeks from D1 of prior cycle, or > 3 weeks from the scheduled treatment, then the patient will be taken off-treatment.

With the approval of the Principal Investigator, patients may be evaluated in offices of other Associate Investigator's (listed in the protocol) every other cycle starting with pre cycle 4. Study medications will continue to be dispensed by the NIH pharmacy. Restaging scans will be performed at NIH

3.2.5 Dose Modification for Prednisone:

Prednisone dose may be reduced to 5 mg once daily for \geq grade 3 hyperglycemia or other toxicity attributed to prednisone. The dose may not be re-escalated following dose reduction.

Prednisone will be discontinued if untoward and unmanageable toxicity occurs (i.e., GI ulceration, symptomatic hyperglycemia unresponsive to medical therapy) despite dose reduction

to 5 mg per day. If prednisone is discontinued in the absence of disease progression, the patient will continue on satraplatin alone.

4 Correlative studies

4.1 Tissue analysis

Given the nature of this pharmacologic intervention, characterization of the actual biological manipulation will be helpful in understanding the biological effects seen following administration of satraplatin. Tissue samples may be analyzed to achieve this goal. In the recently published International Adjuvant Lung Cancer Trial (IALT) Bio Trial, immunohistochemical analysis to determine the expression of the excision repair cross-complementation group 1 (ERCC1) protein in operative specimens of non-small-cell lung cancer was performed and a benefit from cisplatin-based adjuvant chemotherapy was associated with the absence of ERCC1 (test for interaction, $P=0.009$).[44] When available samples obtained from selected prostate cancer patients may be utilized for ERCC1 staining using a commercially available mouse monoclonal antibody to human ERCC1 (clone 8F1, Neomarkers).

Pharmacokinetic analysis will provide insight into dosing efficacy as it relates to both biological activity and clinical response.

Correlative laboratory studies for this trial will be conducted in the Clinical Pharmacology Section of [name] at the NCI. All patients will have leukocyte collection to evaluate for ERCC1 expression. Patients with accessible disease may have tumor biopsies before and during treatment for ERCC1 protein analysis if feasible.

4.1.1 Accessible tumor biopsy

Biopsies of accessible tumors will be optional, and obtained prior to initiation of therapy and prior to starting cycle 2 as described. Patients should avoid the use of aspirin or non-steroidal anti-inflammatory drugs for 1 week prior to biopsy to ensure safety. Accessible tumors will be defined as those masses which can be safely accessed by a core needle biopsy while posing minimal risk to the patient. These lesions may be cutaneous or palpable or demonstrable under CT or ultrasound guidance. Determination of accessibility and safety will be made jointly by an investigator and a staff member from Special Procedures. Accessible tumors will be defined as those masses which can be safely accessed by a core needle biopsy under CT or ultrasound guidance or while posing minimal risk to the patient. [name] or [name] ([name], [contact], [name]) should be contacted to arrange for sample collection. Biopsies are optional and will be limited to those that are easily accessible and involve minimal risk. The procurement of tissue samples will be discussed with patients at enrollment in the protocol. Biopsies will be obtained prior to initiating Satraplatin and prednisone (0 months), and after cycle 1. Participation in the phase II study is in no way contingent on consent to biopsy. If tissue is obtained from biopsies, the expression of ERCC1 will be assessed via immunohistochemical staining using commercially available antibodies. The tissue expression of ERCC1 will be correlated with patient's response to satraplatin.

4.2 Leukocyte analysis

In addition to the optional direct tumor biopsy, DNA will be isolated from whole blood for genotyping analysis as described in section 4.3 and collection as described in 4.3.2.

Approximately 10 mL of blood will be drawn using a 10mL EDTA tube for DNA extraction.

The DNA will be stored at -80°C until the time of analysis. Approximately 8 mL of blood will be drawn using a 8mL CPT Sodium Citrate tube to isolate leukocytes to be lysed for genotyping analysis as described in section 4.3.2.1. The blood will be centrifuged and the buffy coat layer of white blood cells will be removed, washed and pelleted by centrifugation. The pellet will be frozen for future DNA extraction.

4.3 Genotyping analysis:

Genotyping will be done only on these genes and variants listed in this section:

Polymerase-chain reaction (PCR) followed by either restriction fragment length polymorphism (RFLP) or direct sequencing will be used to genotype the SNPs of ERCC1 Asn118Asn (C>T, rs11615), 8092C>A (3' UTR, rs3212986). Genotyping will not be limited to ERCC1 but may include the following: a) XRCC1 Arg194Trp (C>T, rs1799782), Arg399Gln (G>A, rs25489), and b) PARP1 Val762Ala (T>C, rs1136410).

We have excluded genotyping for XPD to avoid the possible clinical implications for carriers including transmission to offspring, childbearing and in the case of two mutant alleles of germline mutations in Xeroderma pigmentosum group D (XPD).

4.3.1 Patient Population and Scope of Studies

All study participants will have to provide a blood sample for genotyping of ERCC1 and other gene polymorphisms. The scope of the informed consent will also allow for the analysis of additional genes on a study specific basis.

4.3.2.1 Blood collection tubes

Prior to Day 1 of Cycle 1(may be collected at anytime during study if unavailable prior to start of therapy).

- **DNA** - Collect blood in 9 or 10 mL polypropylene tube containing the anticoagulant EDTA
 - SARSTEDT Monovette® EDTA KE (9 mL), Part # 02.1333.001 **or**
 - Becton-Dickinson Vacutainer™ K2E (10 mL), Part # 367525 **or**
 - Greiner Bio-One Vacuette® K3E EDTA K3 (9 mL), Part 455036
- Blood tubes must be gently inverted several times after collection to ensure thorough mixing of EDTA with the sample to prevent clotting.
- **Glass tubes MUST NOT be used** as they may break during transport and freeze-thaw cycles.
- **Heparin MUST NOT be used as an** anticoagulant as it may interfere with downstream genotyping methodology.
- **Buffy Coat** - Collect blood in a 8 mL polypropylene tube containing the anticoagulate sodium citrate

- Becton-Dickinson Vacutainer® CPT™ Cell Preparation Tube with Sodium Citrate, Part # 362761
- Blood tubes must be gently inverted 8-10 times after collection to ensure thorough mixing of sodium citrate with the blood.
- Blood tubes must be stored upright at room temperature until centrifugation.

4.3.2.2 Labeling, Storage, and Tracking

All samples sent to the Clinical Pharmacology Program (CPP) will be barcoded, with data entered and stored in the Patient Sample Data Management System (PSDMS) utilized by the CPP. This is a secure program, with access to the PSDM System limited to defined CPP personnel, who are issued individual user accounts. Installation of PSDMS is limited to computers specified by [name]. These computers all have a password restricted login screen. All CPP personnel with access to patient information annually complete the NIH online Protection of Human Subjects course.

PSDMS creates a unique barcode ID for every sample and sample box, which cannot be traced back to patients without PSDMS access. The data recorded for each sample includes the patient ID, name, trial name/protocol number, time drawn, cycle time point, dose, material type, as well as box and freezer location. Patient demographics associated with the clinical center patient number are provided in the system. For each sample, there are notes associated with the processing method (delay in sample processing, storage conditions on the ward, etc.).

4.4 Protocol Completion/Sample Destruction

Barcoded samples are stored in barcoded boxes in a locked freezer at either -20 or -80°C according to stability requirements. These freezers are located onsite in the CPP and offsite at NCI Frederick Central Repository Services (Fisher Bioservices) in Frederick, MD. Visitors to the laboratory are required to be accompanied by laboratory staff at all times.

Access to stored clinical samples is restricted. Samples will be stored until requested by a researcher named on the protocol. All requests are monitored and tracked in the PSDM System. All researchers are required to sign a form stating that the samples are only to be used for research purposes associated with this trial (as per the IRB approved protocol) and that any unused samples must be returned to the CPP. It is the responsibility of the NCI Principal Investigator to ensure that the samples requested are being used in a manner consistent with IRB approval.

Following completion of this study, samples will remain in storage as detailed above. Access to these samples will only be granted following IRB approval of an additional protocol, granting the rights to use the material.

If, at any time, a patient withdraws from the study and does not wish for their existing samples to be utilized, the individual must provide a written request. Following receipt of this request, the samples will be destroyed (or returned to the patient, if so requested), and reported as such to the IRB. Any samples lost (in transit or by a researcher) or destroyed due to unknown sample integrity (i.e. broken freezer allows for extensive sample thawing, etc.) will be reported as such to the IRB.

5 Protocol Evaluation

5.1 BASELINE EVALUATION

- All patients who are deemed eligible and who sign an informed consent will be enrolled in this trial.
- A complete history and physical examination, including ECOG performance status (see Appendix A), will be done within 16 days of enrollment.

5.2 Laboratory Studies (see also Appendix C – Study Calendar)

- Serum PSA
- CBC with differential
- Serum chemistries (Na^+ , K^+ , Cl^- , CO_2 , glucose, BUN, creatinine, albumin, calcium, magnesium, phosphorus, alkaline phosphatase, ALT, AST, total bilirubin, glucose, total protein, LDH)
- -Serum testosterone level

5.3 IMAGING SUTIDES

Non-invasive imaging has become a standard tool in the clinic to monitor primary and metastatic solid tumors. CT scan and bone scan will be performed on all patients at study entry and after every 2 cycles to assess clinical response to satraplatin and prednisone. However, CT scan will only be obtained if baseline CT shows positive disease.

6 Concurrent Therapies

Concurrent hormonal therapy with GnRH agonists to achieve testosterone suppression will be allowed. Concurrent anticancer treatment with chemotherapy, radiation therapy, major surgical procedures for prostate cancer, and nonprotocol-related immunotherapy will not be permitted. No growth factor support will be given prophylactically prior to starting satraplatin.

Patients who require hematopoietic growth factor support (e.g. epogen, darbepoetin), NSAIDs and other maintenance medications prior to study entry will be allowed to continue their supportive therapies. Filgrastim and sargramostim or other bone marrow stimulants are permitted when clinically indicated only after the first cycle.

Premedication will be used with the initiation of therapy following Clinical Center Anti-emetic guidelines and administered 30 – 60 minutes prior to study therapy. If granisetron is used, additional anti-emetics must be taken 8 hours after granisetron dose. Other anti-emetics, take as prescribed.

6.1 Nausea

Should patients develop persistent nausea, they will be given appropriate antiemetic therapy following clinical center guidelines. If this agent proves ineffective, the PI may use another antiemetic regimen (i.e. ondansetron, tropisetron or dolasetron). The type and period of all antiemetic therapy as well as any other concomitant medication administered will be recorded in the case report forms (CRF).

6.2 Diarrhea

Patients can be given loperamide for diarrhea

6.3 Analgesics for pain

Patients may use any analgesic for the treatment of pain, including narcotic and non-narcotic agents.

6.4 Concurrent use of bisphosphonates will be allowed

7 Criteria for Removal from protocol Therapy and Off Study Criteria

7.1 Criteria for Removal from Protocol Therapy

- Clinical progression of disease, appearance of one or more new lesions and/or unequivocal progression of existing lesions.
- Clear radiographic progression of disease by RECIST Criteria version 1.0
- Grade 3 or greater toxicity attributed to treatment, as defined in section 3.3 that does not resolve to grade 1, or pre-treatment baseline, within 3 weeks from next scheduled cycle.
- Neutropenia ($\leq 0.5 \times 10^9/L$) or thrombocytopenia ($\leq 25 \times 10^9/L$) that occurs despite dose reduction to 40mg/m²/d, or if there is retreatment delay of > 8 weeks from Day 1 of previous cycle
- Grade 4 vomiting or diarrhea that cannot be controlled by medical treatment and that occurs after one dose reduction will warrant discontinuation of satraplatin.
- Intolerable or limiting toxicity while on dose reduction of 40 mg/m².
- Intercurrent illness or medical circumstances. If at any time the constraints of this protocol are detrimental to the patient's health, the patient may be removed from protocol therapy and reasons for withdrawal will be documented.
- Patient requests to be taken off treatment. Reasons for withdrawal will be documented.
- Noncompliance with protocol guidelines (patient removed at discretion of Principal Investigator).
- General or specific changes in the patient's condition render the patient unacceptable for further treatment in the judgment of the investigator.
- Subject death.
- Patients who meet criteria for PSA progression may continue on treatment unless they meet the above criteria.

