3.2 Treatment Modifications

Toxicities will be described using the Common Terminology Criteria for Adverse Events version 3.0 (CTCAE v3). The following adjustment will only apply if the toxicities reported are attributed by the investigator to be related to satraplatin and prednisone therapy.

3.2.1 Dose modification for satraplatin:

Dose reductions will be according to the following rules for satraplatin:

For Grade 1 toxicity, no treatment interruption or dose reduction for either satraplatin or prednisone, will be made. For Grade 2 or greater toxicity, subsequent treatment with satraplatin will be followed as shown in the table below and following the dose reduction schema.

Non-Hematologic toxicity Dose adjustments and reductions		
Grade of Non-hematologic toxicity (CTCAE v3.0)	Management/dose adjustment	Dose reduction
Grade 1	None	None
Grade 2 nausea, vomiting or diarrhea	Maintain dosing with symptomatic treatment; Repeat dosing if all tablets appear in emesis	None
Persistent Grade 2 nausea, vomiting or diarrhea despite symptomatic treatment that remains unacceptable (intolerable) to the patient	Decrease from 80mg/m ² to 60 mg/m ² **	Decrease by 20 mg/m ²

Non-Hematologic toxicity Dose adjustments and reductions		
Grade of Non-hematologic toxicity (CTCAE v3.0)	Management/dose adjustment	Dose reduction
Grade 3 clinical, Grade 3 or 4 laboratory abnormalities which are associated with clinical signs and symptoms that are felt to be drug-related	Hold satraplatin and reevaluate the patient at least weekly until toxicity improves to \leq Grade 1 or pre-treatment baseline*	Decrease by 20 mg/m ² (i.e., if patient is at 80mg/m ² /day dose, decrease to 60mg/m ² /day)**
Grade 4 clinical (except pulmonary embolism without significant hypoxia and hemodynamic instability)	Off-study	
Grade 4 vomiting or diarrhea that can not be controlled by medical treatment and that occurs after one dose reduction	Off-study	

*Treatment delay should not be >8 weeks from Day 1 of prior cycle or >3 weeks from the start of next scheduled cycle; otherwise, patient will be taken off-treatment.

**If patient is already at 60mg/m², decrease further to 40mg/m²; No further dose reduction after 40mg/m² will be permitted

-Non-hematologic toxicity ascribed to study drugs must resolve to baseline or \leq grade 1, with the exception of alopecia; or \leq grade 2 for pain in order for re-treatment to continue.

3.2.2 Hematologic Toxicity:

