Given that hematologic toxicity is one of the major toxicities that may be experienced, all patients should have complete blood count measured and recorded weekly during the first 3 cycles and as needed, thereafter. However, if the ANC is $\leq 0.5 \times 10^9/L$ or platelets are $\leq 25.0 \times 10^9/L$, CBC with differential must be redrawn more frequently, at least two times per week, until resolved.

Dose changes for satraplatin will be made based only on changes in the neutrophil and platelet counts. Satraplatin will be discontinued if neutropenia ($\leq 0.5 \times 10^9/L$) lasting ≥ 5 days or thrombocytopenia ($\leq 25 \times 10^9/L$) lasting ≥ 5 days despite dose reduction to 40mg/m²/d occurs, or if there is retreatment delay of > 8 weeks from Day 1 of prior cycle, due to study drug-related hematologic toxicities.

No growth factor support will be given prophylactically prior to starting satraplatin.

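### Section 7.1 removes a patient whose attributed grade 3 pain settles at grade 2 above baseline, while section 3.2.4 allows that patient to be retreated; the section 3.3 that 7.1 cites does not exist

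*Protocol*

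**What the plan says.** Four places in the protocol govern what happens after a toxicity attributed to treatment.

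- **Section 7.1** lists, as a reason for removal from therapy, "Grade 3 or greater toxicity attributed to treatment, as defined in section 3.3 that does not resolve to grade 1, or pre-treatment baseline", with the time limit "within 3 weeks from next scheduled cycle". Pain is not excepted.
- **Section 3.2.4** sets the conditions for the next cycle. Its non-hematologic criterion begins "Non-hematologic toxicity ascribed to study drugs must resolve to baseline or" and goes on to grade 1 or below, with alopecia excepted. It then relaxes the limit for one toxicity: "grade 2 for pain in order for re-treatment to continue".
- **Section 3.2.1, table, grade 3 row**, says "Hold satraplatin and reevaluate the patient at least weekly until toxicity improves to" grade 1 or below, or pre-treatment baseline. The row does not mention pain.
- **Section 3.2.1, note under the table**, repeats the section 3.2.4 criterion, including the grade 2 allowance for pain.

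The scope by attribution is the same throughout. Section 3.2 opens with "The following adjustment will only apply if the toxicities reported are attributed by the investigator to be related to satraplatin and prednisone therapy", and sections 3.2.4 and 7.1 are likewise limited to toxicity ascribed to treatment.

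**The concern.** A removal rule and a re-treatment rule should meet without overlap: a patient who satisfies the conditions for another cycle should not also satisfy the conditions for coming off therapy. For pain the two rules use different grades. Whether such a patient continues satraplatin would then depend on which section the investigator opens, and two investigators following the protocol faithfully could act in opposite ways. That affects patient safety and consistent conduct.

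Section 7.1 makes this harder to resolve by defining the toxicity through section 3.3. The contents list and the body have only 3.1 and 3.2 within section 3.

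**Working it through.** No sample size, power or error rate is involved. The check is a comparison of the texts plus one sum for the time windows.

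**Step 1. Is the conflict one of timing?** Section 3.2.4 allows the next cycle no sooner than 35 days after day 1 of the previous one. Section 7.1 allows 3 weeks from the next scheduled cycle. 35 + 21 = 56 days = 8 weeks, which equals the maximum hold in section 3.2.4 (8 weeks from day 1, or 3 weeks from the scheduled treatment). The windows agree, so any conflict lies in the grade.

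**Step 2. Compare the grade required.**

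| Place | Decision | Attributed non-hematologic toxicity in general | Attributed pain |
|---|---|---|---|
| 3.2.1, grade 3 row | Hold | Grade 1 or below, or baseline | Same; no exception stated |
| 3.2.1, note under table | Re-treat | Grade 1 or below, or baseline (alopecia excepted) | Grade 2 or below is enough |
| 3.2.4 | Re-treat | Grade 1 or below, or baseline (alopecia excepted) | Grade 2 or below is enough |
| 7.1 | Remove | Not at grade 1 or baseline after 3 weeks | Same; no exception stated |

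Apart from pain and the alopecia exception, the rows agree.

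**Step 3. Follow one patient.** Baseline pain is grade 0 or 1. Attributed pain reaches grade 3, falls to grade 2 by day 35 and is still grade 2 at day 56.

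- Section 3.2.4: the pain criterion is met at day 35, so he may be retreated if the other criteria are met.
- Section 3.2.1, grade 3 row read alone: satraplatin stays on hold.
- Section 7.1: he is not removable at day 35. Once day 56 has passed he is removed. Read literally, this applies even if he was retreated at day 35.

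**Step 4. Does the cited definition settle it?** Section 3.3 is absent. Section 3.1.1 also refers to section 3.3 for satraplatin dose modifications, and these now stand in 3.2, so 3.2 is probably what was meant. Following that lead does not remove the conflict, because 3.2 contains the pain allowance that 7.1 omits.

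**The case against.** **The note qualifies the table.** A specific note under a table ordinarily modifies its rows, so section 3.2.1 need not contradict itself. This has force. The grade 3 row is better described as silent on the exception than as opposed to it. The conflict between 3.2.4 and 7.1 remains.

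**The case is rare.** The pain must be attributed to treatment, reach grade 3, fall only to grade 2, exceed baseline, and last 3 weeks past the scheduled cycle. Pain from the cancer itself is outside both rules, and pre-existing pain falls under the baseline clause. This stands and limits the size of the point. The case is still plausible: section 13.1.7 lists chest, back, extremity and bone pain, arthralgia and myalgia for satraplatin.

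Three stronger readings are tempting, and the protocol does not support them.

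- *That section 3.2.4 looks only at neutrophils and platelets.* This is true only of its hematologic criterion. The separate non-hematologic criterion matches 7.1 apart from pain and alopecia.
- *That attributed anemia raises the same conflict.* Section 3.2.2 does say "Dose changes for satraplatin will be made based only on changes in the neutrophil and platelet counts", and the 7.1 bullet names no such limit. However, that bullet closely follows the grade 3 row and 3-week footnote of the table for non-hematologic toxicity, and the next 7.1 bullet deals with neutropenia and thrombocytopenia. The natural reading is one bullet for each kind. The missing section 3.3 only prevents the reader from confirming this.
- *That the wording biases 6-month progression-free survival.* Removal from therapy is neither progression nor leaving the study: section 7.3 ends participation only at death or by the patient's decision, and section 7.2 provides an evaluation within a month for patients stopped for toxicity. Any weakness in imaging after treatment would apply to every removal reason in 7.1 and would not come from this wording.

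**Conclusion.** The point holds for pain. Two stated rules give opposite decisions on continuing satraplatin for the same patient, one from day 35 and the other after day 56. The removal rule also rests on a section that does not exist, so it cannot be confirmed from the text whether the bullet is limited to non-hematologic toxicity.

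The conclusion assumes that the 7.1 bullet covers attributed pain, which it does on either reading of its scope, and that the patient's baseline pain is below grade 2. The protocol gives no frequency for such patients; the number is probably small. No conflict is claimed for other non-hematologic toxicities or for blood counts, and no effect on the primary endpoint is claimed. This is an inconsistency of wording that should be corrected. Which recovery criterion is clinically right is not judged here.

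**What to change.** Reconcile the section 3.2.1 grade 3 row and the note under that table, section 3.2.4 and the section 7.1 bullet, so that one recovery criterion for pain governs holding, re-treatment and removal. The simplest drafting is to state the criterion once and have the other places refer to it. Replace the reference to section 3.3 in 7.1 with the correct section, and make the same correction in 3.1.1. State whether the 7.1 bullet covers non-hematologic toxicity only. The choice of criterion is the sponsor's clinical decision.

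The cost is a few lines of wording in an amendment. No procedure, visit or patient is added.
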